4.3.2. Secondary Endpoints

Several secondary endpoints will be collected to evaluate what effect, if any, the interventions have on each measure.

Analyses may also explore the effect of the actual intervention(s) received on these secondary endpoints. Secondary efficacy endpoints for the following outcome measures will be assessed at 3 months after start of treatment, unless otherwise stated:

- Proportion success evidenced by $\geq 30\%$ reduction in pain interference as measured using Question #9 of the BPI-SF (BPI-9) compared to baseline
- Proportion with clinically significant change (≥ 10 -point reduction) in disability as measured using the Oswestry Disability Index (ODI) compared to baseline
- Durability of primary endpoint, proportion success with $\geq 50\%$ reduction in average back pain intensity, at 6- to 24-months after start of treatment
- Proportion success with $\geq 50\%$ reduction in worst back pain intensity as measured using Question #3 of the BPI-SF (BPI-3) compared to baseline
- Average Patient Global Impression of Change (PGIC)

- Average change in health-related quality of life as measured using the EQ-5D compared to baseline
- Average change in analgesic medication usage (e.g., opioids, non-opioids, and total analgesic medication usage)

Brief Pain Inventory-Short Form (BPI)

The BPI is a widely used assessment designed to measure pain intensity and the interference of pain on daily activities and moods (Cleeland and Ryan 1994). The BPI is recommended by the Initiative on Methods, Measurement, and Pain Assessment in Clinical Trials (IMMPACT) panel and has demonstrated validity and reliability across many cultures and languages (51, 52). The IMMPACT panel was assembled to develop consensus recommendations to improve and standardize the design and conduct of clinical trials involving treatments for pain. Invited participants included academic centers, regulatory agencies, the National Institutes of Health, the US Veterans Administration, and industry representatives. Individual questions of the BPI (e.g., “average pain” (BPI-5), “worst pain” (BPI-3), and “pain interference” (BPI-9)) may be assessed during visits at various time points, including: baseline, follow-up visits, and take-home diaries. When answering BPI questions, subjects will be asked in the question to focus on their back pain or other pain (e.g., leg pain). The site may make arrangements as needed to collect BPI scores if subjects fail to submit their responses (e.g., call to remind the subjects to complete or turn in their diary, mail paper or electronic diaries for BPI question completion, or call and ask questions from the BPI verbally).

Oswestry Disability Index (ODI)

The ODI is a short, widely used assessment designed to measure the degree of disability in patients with low back pain. This validated questionnaire includes topics concerning the intensity of pain, the subject's ability to perform normal daily activities such as personal care, walking, sitting, or standing, and how pain affects the subject's sex life, social life, and travel (53). The ODI will be administered at baseline and follow-up visits. This assessment will provide important information on how disability caused by pain changes during and after treatment with stimulation or standard treatment with RFA.

Health-related quality of life (EQ-5D)

The EQ-5D survey is a standardized instrument measuring health-related quality of life and generic health status. The health status description is measured in five dimensions: mobility, self-care, usual activities, pain/discomfort, and anxiety/depression, and the evaluation asks responders to report their overall health status on a visual analog scale (VAS). The EQ-5D is one of the most commonly cited preference based measures and becoming the gold standard for cost-effectiveness and value assessment (Chapman et al. 2011). The EQ-5D will be assessed at baseline and follow-up visits.

Patient Global Impression of Change (PGIC)

[figure not shown]
Participant ratings of global improvement are one of the core outcome domains in chronic pain studies (52). The Patient Global Impression of Change (PGIC) Scale will be administered at monthly follow-up visits to assess subject perception of overall improvement. The PGIC Scale asks subjects to rate their improvement with treatment on

a 7-point scale that ranges from "very much worse" to "very much improved". The scale provides subjects the opportunity to combine all of the components of their experience into one overall measure and allows clinicians to assess the clinical significance of each subject's improvement or worsening over the course of the study.

Analgesic medication usage

The amount and type of analgesic used by the subject will be recorded daily in diaries at baseline and during the week of each follow up visit. Specific analgesic information that will be collected may include dosages of all narcotic or non-narcotic analgesic pain medications. Narcotic usage may be converted into a morphine equivalent dosage (MED). The use of any other methods of pain relief will also be recorded. This information will be used to assess any changes in medication usage required by the subject and average changes in medication between groups. Opioid, non-opioid and total analgesic medication usage will be analyzed separately.

4.3.3. Exploratory Analysis

113

10. *Journal of the American Statistical Association*, 1990, 85, 1302-1313.

11. **What is the primary purpose of the *Journal of Clinical Oncology*?**

A solid black rectangular redaction box, likely used to obscure sensitive information in a document.

4.4. Amending the Protocol

This study will be carried out in accordance with this Study Protocol/Investigational Plan. SPR Therapeutics will prepare written amendments to revise the protocol, if necessary.

5.0 STUDY PROCEDURES

The study procedures for this protocol are classified according to the following time periods: Consent/Baseline; Diagnostic Procedures and Treatment; and Follow up. Appendix A provides a summary of the study design and overview of subject participation flow. Appendices B.1-B.3 provide a schedule of the study procedures. Appendix C includes the subject participation flow chart

SPR Therapeutics, Inc.
0151-CSP-000

CONFIDENTIAL
Page 21 of 62

5.1. Visit 1 – Consent

Potential subjects will receive a detailed explanation of study specific procedures as well as the risks and benefits of participating in the study. The subject will be asked to sign the approved study consent form during this visit if he/she would like to participate. If the subject agrees to participate by signing the consent form, inclusion/exclusion criteria will be verified by completing the eligibility form and then baseline information will be collected and recorded on the appropriate case report form (CRF).

The consent form will be kept with the study records, and a copy of the consent will be given to the subject. A notation should be made in the subject's medical record of participation in the study, and a copy of the consent may be placed in the hospital record.

The following measures will be assessed:

- Selected questions from Brief Pain Inventory (BPI) (e.g., BPI-3, BPI-5, BPI-9)
- Oswestry Disability Index (ODI)
- Health-related quality of life (EQ-5D)
- Low back pain treatment and diagnostic testing history
- [REDACTED]
- [REDACTED]
- Beck Depression Inventory (BDI-II)
- [REDACTED]
- [REDACTED]
- Key demographic information

A weekly diary will be distributed at this visit for daily recording of baseline back pain via "average pain" (BPI-5), "worst pain" (BPI-3), and analgesic usage prior to randomization. Subjects may be contacted to be reminded of the upcoming Visit 2 date and to review the baseline diary for contents and completion.

5.2. Visit 2 – Randomization

Visit 2 will be conducted upon completion of the baseline diary. The following measure will be assessed:

- Selected questions from Brief Pain Inventory (BPI) (e.g., BPI-3, BPI-5)

Randomization will occur after the following criterion has been met:

- All subjects must have completed all 7 days of the 7-day baseline diary to be eligible to continue participation in the study. The mean "average pain" (BPI-5) score from this diary will be calculated to confirm eligibility (i.e. "average pain" ≥ 4) prior to randomization. If the calculated mean "average pain" from the first week diary is < 4 , the subject will be considered a screen failure, excluded from the study, and will not proceed with the remainder of the visit or study. The diary may be collected either in-person, by mail/email, or completed electronically. If the diary

is collected electronically or by mail/email, Visit 2 may be completed over the phone.

Subjects who meet this additional inclusion criterion will be considered eligible for the study. Qualifying individuals will be randomized in a 1:1 scheme using block randomization to Group 1 (8 weeks of percutaneous PNS therapy following MBB) or Group 2 (standard interventional management). [REDACTED]

Following randomization and completion of Visit 2, all subjects will return to receive a medial branch block or other diagnostic procedure, as appropriate (named Visit 3), before progressing to receive their randomized treatment at Visit 4 (i.e., either SPRINT PNS lead placement for Group 1 or standard interventional management (e.g., RFA, SCS, surgery, etc.) for Group 2.

5.3. Visit 3 – Medial Branch Block or Diagnostic Procedures

A diagnostic medial branch block (MBB) or other diagnostic procedure (e.g., SCS trial, imaging, etc.), as deemed appropriate by the physician for subjects in Group 2, will be completed at or following Visit 3. Visits 2 and 3 may occur on the same day.

The following measures will be assessed at this visit for both groups:

- Selected questions from Brief Pain Inventory (BPI) (e.g., BPI-3, BPI-5)
- Current pain treatments/analgesic usage

GROUP 1 – Medial Branch Block

Subjects will undergo a standard diagnostic medial branch block (MBB) targeting the area where they have chronic low back pain. Provocative maneuvers or positions which normally exacerbate their typical pain may also be assessed and documented before and after the procedure to help determine effect of MBB.

The diagnostic medial branch block (MBB) will be performed according to standard practice using aseptic technique. [REDACTED]

[REDACTED]

[REDACTED]

[REDACTED]

[REDACTED]

Pain scores will be collected post-procedure to evaluate the impact of the MBB. Subjects in Group 1 (PNS) will proceed to Visit 4 (PNS Lead Placement) after a single MBB (Visit 3), regardless of the outcome.

If a subject has previously undergone a diagnostic lumbar medial branch block (MBB) within 3 months of the baseline visit, and results and medical records are available from that block, a subject is not required to complete an additional block at this visit. However, procedure details and results from the procedure should be documented in the CRFs. If a subject previously underwent the MBB and results are not available, the subject should complete the visit, repeating the MBB as part of the study.

GROUP 2 - Diagnostic Procedures

Subjects in Group 2 will receive standard of care diagnostic testing and/or interventions (e.g., Medial Branch Block, SCS trial, MRI, etc.) for their low back pain as they usually would if not participating in the study. All diagnostic tests or interventions received by Group 2 subjects will not be paid for through the study. Subjects should follow their insurance requirements (e.g., prior authorization) for these procedures. [REDACTED]

Additionally, for subjects in Group 2, another MBB or other diagnostic procedure may be repeated at a repeat Visit 3, if necessary. The necessity of a second Visit 3 will be determined by the Investigator and/or subject's Insurance, as is required for them to receive the randomized therapy (standard interventional management deemed appropriate by the investigator).

If a subject has previously undergone a diagnostic procedure (e.g., MBB, MRI, SCS trial, etc. within 3 months of the baseline visit, results and information may be collected to serve as diagnostic procedures completed for Visit 3.

Details will be collected regarding the approaches used for the diagnostic procedure(s), as well as outcomes following the procedure(s), including adverse events.

Subjects in Group 2 will continue to participate in the study visits independent of their successful completion of diagnostic procedures and/or standard interventional management. For example, if a subject does not proceed to receive lumbar RFA because they failed their MBB (e.g., had less than 50% response), they may receive other treatments for their low back pain recommended by their physician and continue to participate in study visits. In this case, the subject will still return to the clinic at Visit 4 to discuss alternative standard interventional management approaches, which will be regarded as the start of Treatment.

5.4. Visit 4 – Treatment (PNS Lead Placement or start of treatment with Standard Interventional Management)

GROUP 1 - PNS Lead Placement

Subjects randomized to Group 1 will undergo the following prior to lead placement:

- Women of childbearing age and reproductive potential will have a pregnancy test completed as part of eligibility confirmation before or at Visit 4.

- Subjects taking anticoagulants may have their medication adjusted as determined by the Investigator to prevent potential excessive bleeding.

Participants who are randomized to Group 1 and meet all Eligibility criteria will undergo placement of the percutaneous leads. The following measures may be assessed prior to lead placement:

- Selected questions from Brief Pain Inventory (BPI) (e.g., BPI-3, BPI-5)
[REDACTED]
- Current pain treatments/analgesic usage

Figure 2 shows a magnetic resonance image (MRI) of the spine and paraspinal musculature.

[figure not shown]

Figure 2: Magnetic resonance image (MRI) of lumbar paraspinal musculature, multifidus (MF) and longissimus (LS) (54).

The most painful regions on each side of the subject's back may be determined
[REDACTED]
[REDACTED] The relevant section of the back will be cleansed and draped using aseptic technique and will not be shaved (cutting hair with scissors or clippers will be

allowed). Local anesthesia may be administered at the insertion site prior to lead placement.

Placement of the leads will be guided by use of ultrasound or fluoroscopy.

region

Leads will be placed in the lumbar

to target the medial branch of the dorsal ramus

Determination of stimulation parameters:
Stimulus parameters will be varied over a range of parameters [REDACTED]

[REDACTED] Stimulation intensities will be delivered within
ranges that have been demonstrated not to cause tissue damage [REDACTED]
[REDACTED]. Optimal stimulus settings will be set by the site staff prior to the end of the visit
(Visit 4) and may be adjusted as needed throughout the study.

Stimulation parameters may be varied. [REDACTED]

[REDACTED] Safeguards on the device ensure the
subject cannot exceed the acceptable safety ranges for stimulation. The care and

maintenance of the stimulation system, leads, and lead exit sites will be performed by members of the clinical or study staff. Subjects will also be provided with a manual and instructed on the use and care of the device in case changes are required when clinical/study staff is not present. Subjects will be encouraged to enlist assistance from a caregiver for monitoring skin and changing bandages. However, subjects may also request visits to the clinical site for monitoring of skin and/or bandage changes by study staff.

Sterile, waterproof covering bandages [REDACTED] will be placed over the exit sites of the leads. [REDACTED]

[REDACTED] The clinical/study staff and subject will be instructed to inspect the electrode exit site for signs of irritation and report them to the clinician. [REDACTED]

The area around the leads and surface electrodes will be kept clean and dry. If bandages become wet or loose, the bandages will be changed. [REDACTED]

[REDACTED]

[REDACTED]

[REDACTED]

[REDACTED]

Data regarding the specific details of the lead placement procedure will be collected during this visit and recorded on the appropriate CRF. Images (e.g., photographic, video, ultrasound) may be collected to provide a visual record of the locations of electrodes/leads and anatomy. Subject consent will be obtained for photography or video recording, and subjects will be de-identified in photos or videos.

GROUP 2 - Standard Interventional Management

Subjects in Group 2 will receive standard interventional management for the treatment of their low back pain, as usual, at the discretion of the site investigator. Visit 4 is not required to be completed on the exact day of the intervention; subjects may return for the visit on a separate day.

The following measures will be assessed:

- Selected questions from Brief Pain Inventory (BPI) (e.g., BPI-3, BPI-5)
[REDACTED]
- Current pain treatments/analgesic usage

Details will be collected regarding the approaches used for intervention (e.g., system manufacturer, parameters, location, etc), as well as outcomes following the procedure. Subjects in Group 2 will continue to participate in the study visits independent of their successful completion of diagnostic testing and/or standard interventional management procedure(s) (i.e., even if a subject does not proceed to receive RFA, SCS, or surgery, they may continue to participate in study visits).

It is possible that treatment with standard interventional management may not be completed at this visit (e.g., if multiple nerves and/or levels are to be ablated with RFA during the procedure, or additional treatments or procedures are required). Thus, at the conclusion of this Visit, a subject will proceed to treatment phase. The subject will receive care as usual following the procedure and return for study visits according to the visit schedule. The subject may return as needed to complete additional diagnostic or interventional procedures throughout the study. In this scenario, the subject will still maintain the schedule of visits starting from the first Visit 4.

Subjects may elect not to undergo a diagnostic procedure and/or treatment (e.g., subject elects to continue their usual care for back pain) but are still willing to remain in the study. In this event, if the subject has not undergone a diagnostic procedure by the end of the Visit 3 window, they will progress directly to Visit 4 (i.e., Visit 3 will be marked as "missed" and Visit 4 will be completed via phone). Regardless of the mode of participation, subjects who continue participation through 12 months after "Start of Treatment" (completion of Visit 16) will be eligible for crossover.

Subjects in Group 2 who receive standard interventional management may be eligible to receive treatment with PNS as part of the study via crossover after 12 months (Visit 16).

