4.2.6. Sample Size & Justification

Up to 30 sites will participate in the study. The study will be planned with a maximum sample size of 230 enrolled subjects

Subjects will be randomized to either Group #1 or Group #2 using a 1:1 randomization scheme.

All subjects who sign a consent will receive a subject ID number. Subjects who sign a consent and do not meet all study eligibility criteria will be considered screen failures and not count against the number of enrolled subjects. Subjects who are randomized at Visit 2 will be counted as enrolled. If a subject does not receive the randomized intervention (e.g., complete PNS or receive a standard interventional procedure), their results may be excluded and/or analyzed separately from the rest of the population.

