4.3.1. Primary Endpoints

4.3.1.1. Primary Efficacy Endpoint

The primary outcome of this study will be calculated as the mean score of average daily back pain intensity 3 months after start of treatment to baseline. This will be recorded using Question 5 of the Brief Pain Inventory Short Form (BPI-5; details of BPI below), which assesses “average pain” on an 11-point numerical rating scale, with one end

representing “no pain” (0) and the other end representing “pain as bad as you can imagine” (10). Subjects will record BPI-5 scores daily in a diary, and the mean score for each week will be calculated for each subject. The primary endpoint will be a highly clinically significant reduction in back pain evidenced by $\geq 50\%$ reduction in mean “average pain” (BPI-5) over the week prior to the 3-month follow-up visit (Visit 13) compared to baseline.

The primary endpoint compares the proportion of subjects in Group 1 (PNS) relative to that in Group 2 (standard interventional management) that achieve $\geq 50\%$ reduction in average back pain intensity from baseline to 3-months after start of treatment. This endpoint will examine the statistical non-inferiority of the proportion of clinical successes in Group 1 compared to Group 2, and if non-inferiority is achieved, examine the statistical superiority of the proportion of successes in Group 1 compared to Group 2.

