8.0 DATA ANALYSIS AND STATISTICAL METHODS

All primary and secondary outcome data will be analyzed and reported. Each clinical site or individual clinician may be analyzed separately. The study objective is to compare the safety and effectiveness of percutaneous PNS for the treatment of low back pain to standard interventional management. The study will determine if the treatment effect of percutaneous PNS is equivalent (i.e., statistically non-inferior), and if so, if it is superior, to standard treatment with standard interventional management.

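### Group 2 subjects may go without any interventional procedure, and a discretionary rule decides whether they count in a non-inferiority claim worded against standard interventional management

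*Protocol*

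**What the plan says.** **The claim.** Section 4.3.1.1 states: "This endpoint will examine the statistical non-inferiority of the proportion of clinical successes in Group 1 compared to Group 2". If that succeeds, superiority is tested. The same section labels Group 2 as a whole standard interventional management. Section 8.0 says the study will determine whether the PNS effect is "equivalent (i.e., statistically non-inferior), and if so, if it is superior, to standard treatment with standard interventional management".

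**What Group 2 may receive.** Section 5.3 says "Subjects in Group 2 will continue to participate in the study visits independent of their successful completion of diagnostic procedures" or of the interventional management itself. A subject who fails the medial branch block and so does not have RFA returns for a Visit 4 discussion of alternatives, and that discussion counts as the start of treatment. Section 5.4 keeps subjects who never have RFA, SCS or surgery. It also says, and section 8.1 repeats: "Subjects may elect not to undergo a diagnostic procedure and/or treatment". In that case Visit 3 is recorded as missed and Visit 4 is done by telephone. The primary endpoint is measured from that starting point, as the change in "average back pain intensity from baseline to 3-months after start of treatment".

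**How non-receivers are analyzed.** Section 4.2.6 says of a subject in either arm who does not receive the randomized intervention that "their results may be excluded and/or analyzed separately from the rest of the population". Sections 4.2.6 and 7.5 count everyone randomized at Visit 2 as enrolled. Section 7.4 classes a consented subject who does not go on to treatment procedures as a screen failure, and does not limit this to the period before randomization.

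**The concern.** The protocol leaves three outcomes open for a randomized subject with no procedure: included in the assigned arm, excluded or analyzed separately, or possibly treated as a screen failure. Each changes what the primary comparison means.

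If these subjects are kept, and usual care does less well than a delivered procedure, the Group 2 success rate falls below that of the interventions named in the claim. Non-inferiority and superiority both become easier to show relative to those interventions.

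If they are dropped at discretion, the arms are no longer those formed by randomization. The decision could also be taken with results in view: section 5.11 says results are evaluated throughout the study and can lead to early stopping, and the arms are visibly different.

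Non-receipt need not be balanced. Under section 5.3, Group 1 goes on to PNS after one block whatever its result. Group 2 procedures are not paid for by the study and depend on diagnostic results and insurance requirements.

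**Working it through.** **The plan's own figure.** Section 4.2.6 says: "The study will be planned with a maximum sample size of 230 enrolled subjects", randomized 1:1, so 230 / 2 = 115 per arm. The visible text gives no margin, alpha, power or success rates. The 230 therefore cannot be re-derived, and it is not called wrong.

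**Assumptions (none from the protocol).** Success with a delivered control procedure p = 0.50. Success on usual care without a procedure u = 0.35 or 0.20. Margin M = 0.10 or 0.15. One-sided 2.5% test with unpooled variance. Share without a procedure f = 0 to 0.30. PNS is set exactly M below a delivered control, pT = p - M, so it is just inferior to the interventions themselves.

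**Case A: non-receipt in Group 2 only.**
- Control rate: pC = (1 - f)p + f·u.
- Then pT - pC + M = f(p - u), so the effective margin against a delivered control is M + f(p - u).
- P(declare non-inferiority) ≈ Φ( f(p - u)/SE - 1.96 ), with SE = √[ pT(1 - pT)/115 + pC(1 - pC)/115 ].
- Example, M = 0.15, u = 0.20, f = 0.20: pC = 0.8 × 0.50 + 0.2 × 0.20 = 0.44 and pT = 0.35. SE = √(0.2275/115 + 0.2464/115) = 0.0642. Then 0.06/0.0642 - 1.96 = -1.03, so P ≈ 15.3%. Exact binomial enumeration gives 14.8%. The effective margin is 0.15 + 0.06 = 21 points.

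**Case B: the same share f in both arms.** Now pT = (1 - f)(p - M) + f·u, so pT - pC + M = f·M. The shift no longer depends on u and is smaller: 0.2 × 0.15 = 0.03 instead of 0.06 in the example.

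**Exact results** (each range covers M = 10 and 15 points):

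| Share without a procedure | A, usual care 35% | A, usual care 20% | B, usual care 20% |
|---|---|---|---|
| 0% | 2.3-2.4% | 2.3-2.4% | 2.3-2.4% |
| 10% | 3.9-4.0% | 6.4-6.5% | 3.4-4.0% |
| 20% | 6.4-6.5% | 14.6-14.8% | 4.9-6.6% |
| 30% | 9.8-10.0% | 28.2-28.6% | 7.0-10.6% |

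The unseen margin hardly matters in case A. The share without a procedure and the gap p - u drive the result. These ranges are not bounds: with p = 40-60%, M = 10-20 points and u = 10-20%, the normal approximation for case A gives 5-12%, 9-33% and 16-64%.

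**Superiority.** If PNS only equals a delivered control at 50%, with u = 0.20 and non-receipt in Group 2 only, superiority is declared in about 16% of trials at f = 0.20 and 29% at f = 0.30, against 2.8% at f = 0.

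**The case against.** - **The comparator is a care strategy.** The synopsis calls it conventional management, and section 5.4 leaves it to the investigator's discretion. Not having RFA after a negative block is how such a strategy works, and these subjects are on usual care, not untreated. This stands. Judged against the strategy, the worked example is not a false claim: PNS at 35% is 9 points below 44%, inside a 15 point margin. The objection therefore supports analyzing everyone as randomized, but it does not support a conclusion about the interventions themselves.
- **Analysis sets belong in the SAP.** The SAP is not shown and parts of the protocol are redacted, so a firm rule may exist. Its absence is not the point. The protocol itself contains a permissive exclusion sentence and a screen-failure sentence that conflicts with the enrollment rule, and a SAP rule would have to override both.
- **The size is assumed.** This also stands. Milder usual-care results, or non-receipt in both arms, shrink it considerably. Incomplete PNS is foreseeable, since section 8.1 names early lead loss as a cause of data loss.
- **Restricting to recipients brings its own bias.** Block response can select Group 2 recipients but not Group 1 recipients, and section 2.0 ties RFA benefit to block response. This rules out making that analysis a mandatory gate.

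A reader might infer that subjects with no procedure definitely count as treated controls. The documents do not say so: section 4.2.6 allows them to be excluded or analyzed separately, and sections 5.3 and 5.4 govern study visits, not the analysis set.

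**Conclusion.** The concern holds in this form: the protocol permits non-delivery of the control, words the claim against the delivered intervention, and leaves non-receivers in either arm to an open-ended choice, with section 7.4 at odds with sections 4.2.6 and 7.5. Inclusion biases the test towards non-inferiority and superiority relative to delivered interventions. Discretionary exclusion gives up the randomized comparison.

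Under the stated assumptions, the chance of declaring non-inferiority when PNS is worse than delivered interventions by the whole margin is about 4-6%, 6-15% and 10-29% at 10%, 20% and 30% non-receipt in Group 2 only. It is about 3-4%, 5-7% and 7-11% with equal non-receipt, against a nominal 2.5%. The direction needs only that usual care does worse than a delivered procedure and that non-receipt is not concentrated in Group 1.

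It would be wrong to read the upper figure of 29% as the trial's error rate. It needs 30% non-receipt confined to Group 2 and 20% success on usual care, and the protocol gives neither.

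**What to change.** 1. Replace the discretionary sentence in section 4.2.6 with a rule, fixed before any review of results by arm, that the primary analysis includes all randomized subjects as randomized.
2. Reconcile section 7.4 with sections 4.2.6 and 7.5, so that no randomized subject can become a screen failure by not proceeding to treatment.
3. Report, for each arm, the share that received the assigned procedure before Visit 13.
4. Add a pre-specified supportive analysis of subjects who received it. Define which procedures count in Group 2, say how Group 1 subjects who also have another intervention are classed, and note that block response selects Group 2 but not Group 1. It should not gate the primary test.
5. State in advance what counts as agreement. Unless the supportive analysis agrees, limit the conclusion to non-inferiority to a strategy of offered standard interventional management, not to the interventions themselves.

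The cost is wording changes, one extra analysis on data already collected, and a possibly narrower claim. The supportive set is smaller and not protected by randomization.
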